7.4 Tables from Clinician DCF: Safety Data Analysis

These analyses will use Safety Population dataset.

All patients who started the study and received at least one dose of the sarecycline during the study observation period, as part of usual care. This corresponds to the entire cohort of 300 eligible patients who started the study.

Table 4.1 Safety Analysis Population

S1: Population	N=x
Total FAS Population	n (%)
Total Safety Population	n (100%)

Note: Data from Patient DCF

Table 4.2 Study Subject Selection Criteria, Safety Population

Domain (N=X)	Yes	No
SS1r1 Diagnosed with actinic keratoses of the face and/or scalp?	n (%)	n (%)
SS1r2 Has clinically typical, visible, and discrete AK lesions?	n (%)	n (%)
SS1r3 Considered a candidate for tirbanibulin (Klisyri®) AND you plan to administer tirbanibulin (Klisyri®) treatment?	n (%)	n (%)
SS1r4 At least 18 years of age at the time of initiation of tirbanibulin (Klisyri®) treatment?	n (%)	n (%)
SS1r5 Willing to avoid excessive sun or UV exposure, and/or use relevant sunscreen protection and protective clothing during the study duration.	n (%)	n (%)
SS1r6 Able to read and write English.	n (%)	n (%)
SS1r7 Able to provide consent to participate AND is willing to comply with study procedure?	n (%)	n (%)
SS2r1 Have another dermatological condition of the face that could interfere with the actinic keratoses clinical evaluations?	n (%)	n (%)
SS2r2 Hypertrophic AK lesions, open wounds or suspected skin cancers within close proximity of the treatment area	n (%)	n (%)
SS2r3 Anticipated need for in-patient hospitalization or in-patient surgery within the next 2 months.	n (%)	n (%)
SS2r4 Have a medical chart accessible to complete baseline data collection?	n (%)	n (%)

Note: Data from Clinician DCF. The denominator for the percentage is the number of patients with available data (N=X). There are no missing data.

Table 4.3 Patient Demographic Characteristics, Safety Population

Adult Demographic Data	Total (N=x)
S1: Age	Mean, SE (SD) Median Min, Max
S3: Gender	
Male	n (%)
Female	n (%)
Other S3r3oe	n (%)
S4: Marital Status	
Not Married	n (%)
Not Marries, living with Partner	n (%)
Married or Civil Union	n (%)
Divorced or Separated	n (%)
Widow/Widower	n (%)
Prefer not to answer	n (%)
S5: Highest level of Education	
Less than high school diploma/degree	n (%)
High school degree or equivalent (e.g., GED)	n (%)
Some college but not degree	n (%)
Associated degree	n (%)
Bachelor's degree	n (%)
Graduate degree	n (%)
Prefer not to answer	n (%)
S6: Employment status	
Employed/Working full-time (paid)	n (%)
Employed/Working part-time (paid)	n (%)
Homemaker	n (%)
Student	n (%)
Retired	n (%)
Unemployed	n (%)
S7: Annual household income	
\$20,000 or less	n (%)
\$20,001-\$50,000	n (%)
\$50,001-100,000	n (%)
\$100,001 or more	n (%)
Prefer not to answer	n (%)
S8: Regions/States	
Northeast	n (%)
Midwest	n (%)
West	n (%)

South	n (%)
S9: Number of household members	
0	n (%)
1	n (%)
2	n (%)
3	n (%)
4	n (%)
More than 4	n (%)
S14: Primary Health Insurance	
Private health insurance	n (%)
Medicaid	n (%)
Medicare	n (%)
Uninsured	n (%)
S10: Race/Ethnicity*	
S10r1: White	n (%)
S10r2: Black or African American	n (%)
S10r3: American Indian or Alaska Native	n (%)
S10r4: Asian	n (%)
S10r5: Native Hawaiian or other Pacific Islander	n (%)
S10r6: Other	n (%)
S10r7: Prefer not to answer	n (%)
S11: Hispanic, Latino, or of Spanish Origin	
Yes	n (%)
No	n (%)

Table 4.4 Patient Clinical Characteristics from Medical Chart, Safety Population

Character	Statistics	Baseline (N=XX)
PC1 Gender		
Male	n (%)	
Female	n (%)	
Other	n (%)	
PC2 Primary Health Insurance		
Private health insurance	n (%)	
Medicaid	n (%)	
Medicare	n (%)	
Uninsured	n (%)	
Other: Self Pay	n (%)	
Not available	n (%)	
PC3 Height (in inches)	N, Mean, SE (SD), Median, Min, Max	
PC4 Weight (in lbs/pound)	N, Mean, SE (SD), Median, Min, Max	
PC5 Waist circumference (in inches)	N, Mean, SE (SD), Median, Min, Max	
Body Mass Index (BMI - calculated)	N, Mean, SE (SD), Median, Min, Max	
PC6 Blood pressure (in mm HG)		
Systolic	N, Mean, SE (SD), Median, Min, Max	
Diastolic	N, Mean, SE (SD), Median, Min, Max	
PC7 Concomitant (comorbid) conditions		
None	n (%)	
Anxiety	n (%)	
Anemia or other blood disease	n (%)	
Asthma	n (%)	
Atopic dermatitis	n (%)	
Cancer (of any type)	n (%)	
Crohn's disease / IBD	n (%)	
Diabetes	n (%)	
Depression	n (%)	
Dyslipidemia/Hyperlipidemia	n (%)	
Gastroesophageal reflux disease	n (%)	
Heart disease	n (%)	
Hypertension	n (%)	
Kidney disease	n (%)	
Liver damage or disease	n (%)	

Lung disease	n (%)
Osteoarthritis, degenerative arthritis	n (%)
Other gastrointestinal disease	n (%)
Other	n (%)
X Y Z	n (%)

PC8 History of Skin Cancer

Yes	n (%)
No	n (%)

AK2 Fitzpatrick Skin-type classification?

Type I	n (%)
Type II	n (%)
Type III	n (%)
Type IV	n (%)
Type V	n (%)
Type VI	n (%)

Table 4.5 Tirbanibulin Treatment Characteristics for the Original Treated Area, Safety Population

Character	Baseline (N=x)
TH1B: Prescription dose 3. 1% tirbanibulin, single-dose packets 4. Other, please specify [TH1Br2oe] a. X	n (%)
TH1C: Prescription frequency 3. Once daily for 5 consecutive days 4. Other, please specify: [TH1Cr2oe] a. X	n (%)

Table 4.6 Area of Tirbanibulin Treatment for the Original Treated Area, Safety Population

Character	Baseline (N=x)
AK3A1: What is the AK treatment area you have identified for the patient, to apply tirbanibulin (Klisyri®)?	
Left	
Face	n (%)
Scalp	n (%)
Right	
Face	n (%)
Scalp	n (%)
Center	
Face	n (%)
Scalp	n (%)
Unknown	
Face	n (%)
Scalp	n (%)
Overall	
Face (any area)	n (%)
Scalp (any area)	n (%)

Table 4.7 Tirbanibulin Treatment Completion Rate for the Original Treated Area, Safety Population

Character	Week 8 (N=X)
P2: Did the patient complete 5-day treatment course of tirbanibulin (Klisyri®) at the beginning of the study? (N=X)	
Yes	n (%)
No	n (%)

Table 4.8 Prior AK Treatment (To-Date) Including within the Past 6 Months, Safety Population

Character TH2 and TH3 (Start date prior to Klisyri®; End date within the past 6 months or No end date)	Baseline (N=x)
TH2A checked AND TH3=No Has not use any AK medication	n (%)
Topical medication	
[TH2r1] 5-Fluorouracil (5-FU)	
[TH2r2] Salicylic acid	
[TH2r3] Imiquimod	
[TH2r4] Ingenol mebutate	n (%)
[TH2r5] Diclofenac	
[TH2r6] Other [TH2r6oe]	
A	
B	
C	
Oral medication:	
[TH2r7] Isotretinoin	
Other	n (%)
A	
B	
C	
Other therapies:	
[TH2r8] Photodynamic therapy	
[TH2r9] Cryosurgery/Cryotherapy	
[TH2r10] Chemical/acid peel	
[TH2r11] Curettage	
[TH2r12] Laser therapy	n (%)
Other:	
A	
B	
C	

Table 4.9 AK Concomitant Medication Use During the 8-Week Observation Period, Safety Population

Character TH3 with no end date TH3Ar6na checked (end date after Klisyri® start date within the 8 week period)	N=X n (%)
Add Variables from week-8 - start date within 8 week period	
Has not used any acne medication TH3 = No	
Topical medication	
5-Fluorouracil (5-FU)	
Salicylic acid	
Imiquimod	
Ingenol mebutate	
Diclofenac	
Other	
Oral medication	
Isotretinoin	
Other	
Other therapies	
Photodynamic therapy	
Cryosurgery/Cryotherapy	
Chemical/acid peel	
Curettage	
Laser therapy	
Other	

Table 4.10 Non-AK Concomitant Medication Use During the 8-Week Observation Period, Safety Population

Character TH4	N=x
TH4 = No Is not currently on any concomitant medication to manage conditions other than AK medication	
Add Variables from Week-8	
<<categories from WHO ATC classifications>>	
A	n (%)
B	n (%)
C	n (%)
D	n (%)
E	n (%)

Note: Data from Clinician DCF; X patients had missing data; The denominator for the percentages is the number of patients with available data (N=X). This concomitant non-AK medication use correspond to use of medications at any time during the study observation period, overlapping with Klisyri® medication use.

Table 4.11 Patient Disposition Throughout the Study

	Baseline n (%)		Week 8 n (%)		Week 24 n (%)	
	Patient Survey	Clinician Survey	Patient Survey	Clinician Survey	Patient Survey	Clinician Survey
(Cumulative numbers)						
Patients completing study visit						
Patients with missing surveys						
Patient Terminations/ Discontinuations						
P1Br3 Due to Adverse event associated with any medication (other than tirbanibulin (Klisyri®)						
P1Br4 Due to Adverse drug reaction associated with tirbanibulin (Klisyri®)						
P1Br5 Due to Clinician decision: tirbanibulin (Klisyri®) treatment non-compliance						
P1Br6 Due to Clinician decision, Other [P1Br6oe]						
P1Br2 Patient voluntarily withdrawal of consent (for reasons other than adverse event or adverse drug reaction)						
P1Br1 Patient Lost to follow-up						
TOTAL Study Population (N)	300	300	300	300	300	300

Table 4.12 Reason for Discontinuation

Statistics	Adverse drug reaction associated with tirbanibulin (Klisyri®)	Adverse event associated with any medication (other than tirbanibulin (Klisyri®))	Clinician decision: tirbanibulin (Klisyri®) treatment non-compliance	Clinician decision, Other	Patient voluntarily withdrawal of consent (for reasons other than adverse event or adverse drug reaction)	Patient Lost to follow-up	TOTAL
Week 8	n (%)						
Week 24	n (%)						
TOTAL	n (%)						

Table 4.13 Subject Level Summary of Local Site Reactions

LSRs (Refer to annotated CRF for all other variables)	Baseline N=X	Week 8 N=X	Week 24* N=X
LSR1 Erythema (N=X)			
LSR1r1 Grade			
2. Mild	n (%)	n (%)	n (%)
3. Moderate	n (%)	n (%)	n (%)
4. Severe	n (%)	n (%)	n (%)
LSR1r4 Action taken with Tirbanibulin			
1. Drug withdrawal	n (%)	n (%)	n (%)
2. Dose Reduced	n (%)	n (%)	n (%)
3. Dose Increased	n (%)	n (%)	n (%)
4. Dose not changed	n (%)	n (%)	n (%)
5. Not Applicable	n (%)	n (%)	n (%)
LSR2 Flaking/Scaling (N=X)			
Grade			
Mild	n (%)	n (%)	n (%)
Moderate	n (%)	n (%)	n (%)
Severe	n (%)	n (%)	n (%)
Action taken with Tirbanibulin			
Drug withdrawal	n (%)	n (%)	n (%)
Dose Reduced	n (%)	n (%)	n (%)
Dose Increased	n (%)	n (%)	n (%)
Dose not changed	n (%)	n (%)	n (%)
Not Applicable	n (%)	n (%)	n (%)
LSR3 Crusting (N=X)			
Grade			
Mild	n (%)	n (%)	n (%)
Moderate	n (%)	n (%)	n (%)
Severe	n (%)	n (%)	n (%)
Action taken with Tirbanibulin			
Drug withdrawal	n (%)	n (%)	n (%)
Dose Reduced	n (%)	n (%)	n (%)
Dose Increased	n (%)	n (%)	n (%)

Dose not changed	n (%)	n (%)	n (%)
Not Applicable	n (%)	n (%)	n (%)

LSR4 Swelling (N=X)**Grade**

Mild	n (%)	n (%)	n (%)
Moderate	n (%)	n (%)	n (%)
Severe	n (%)	n (%)	n (%)

Action taken with Tirbanibulin

Drug withdrawal	n (%)	n (%)	n (%)
Dose Reduced	n (%)	n (%)	n (%)
Dose Increased	n (%)	n (%)	n (%)
Dose not changed	n (%)	n (%)	n (%)
Not Applicable	n (%)	n (%)	n (%)

LSR5 Vesiculation/Pustulation (N=X)**Grade**

Mild	n (%)	n (%)	n (%)
Moderate	n (%)	n (%)	n (%)
Severe	n (%)	n (%)	n (%)

Action taken with Tirbanibulin

Drug withdrawal	n (%)	n (%)	n (%)
Dose Reduced	n (%)	n (%)	n (%)
Dose Increased	n (%)	n (%)	n (%)
Dose not changed	n (%)	n (%)	n (%)
Not Applicable	n (%)	n (%)	n (%)

LSR6 Erosion/Ulceration (N=X)**Grade**

Mild	n (%)	n (%)	n (%)
Moderate	n (%)	n (%)	n (%)
Severe	n (%)	n (%)	n (%)

Action taken with Tirbanibulin

Drug withdrawal	n (%)	n (%)	n (%)
Dose Reduced	n (%)	n (%)	n (%)
Dose Increased	n (%)	n (%)	n (%)
Dose not changed	n (%)	n (%)	n (%)

Not Applicable	n (%)	n (%)	n (%)
LSR7 Scarring			
Present?			
Yes	n (%)	n (%)	n (%)
No	n (%)	n (%)	n (%)
LSR8 Hypo-pigmentation			
Present?			
Yes	n (%)	n (%)	n (%)
No	n (%)	n (%)	n (%)
LSR9 Hyper-pigmentation			
Present?			
Yes	n (%)	n (%)	n (%)
No	n (%)	n (%)	n (%)

Table 4.14 Subject Level Summary of Local Site Reactions, by Patient ID

Patient ID	Study/ Survey Timepoint	LSR	Grade	Date of Baseline (yyyy/mm/dd)	Date of Onset (yyyy/mm/dd)	Status	Action Taken with tirbanibulin*

Table 4.15 Subject Level Summary of Adverse Events, Any Type

Adverse Events, Any Type	N=X n (%)
Subjects with at least 1 adverse event (any type)	
Intensity of adverse event, among Subjects with at least 1 adverse event (any type)	
Mild	
Moderate	
Severe	
Action taken with Tirbanibulin, among Subjects with at least 1 adverse event (any type)	
Drug withdrawal / study discontinuation	
Other Actions:	
Dose Not Changed	
Subjects with at least 1 SAE or Serious ADR	
Subjects with at least 1 SAE or Serious ADR resulting in death	

Table 4.16 Subject Level Summary of 'Not-Related to Tirbanibulin' Adverse Events

'Not-Related to Tirbanibulin' Adverse Events	N=X n (%)
Subjects with at least 1 'not-related' AE	
Intensity of adverse event, among Subjects with at least 1 'not-related' AE	
Mild	
Moderate	
Severe	
Action taken with Tirbanibulin, among Subjects with at least 1 'not-related' AE	
Drug withdrawal / study discontinuation	
Other Actions:	
Dose Not Changed	
Subjects with at least 1 SAE	
Subjects with at least 1 SAE resulting in death	

Table 4.17 Subject Level Summary of 'Not-Related' AEs by Organ Class & Preferred Term

System Organ Class: Preferred Term	N=X	Intensity	Action Taken
	n (%)	Mild, Moderate, Severe	A: Dose not changed; B: Drug withdrawn.

Table 4.18 Subject Level Summary of Adverse Drug Reactions

Adverse Drug Reactions	N=X n (%)
Subjects with at least 1 ADR	
Intensity of adverse event, among Subjects with at least 1 ADR	
Mild	
Moderate	
Severe	
Action taken with Tirbanibulin, among Subjects with at least 1 ADR	
Drug withdrawal / study discontinuation	
Other Actions:	
Dose Not Changed	
Subjects with at least 1 Serious ADR	
Subjects with at least 1 Serious ADR resulting in death	

Table 4.19 Subject Level Summary of ADRs by Organ Class & Preferred Term

System Organ Class: Preferred Term	N=X	Intensity	Action Taken
	n (%)	Mild, Moderate, Severe	A: Dose not changed; B: Drug withdrawn.

Table 4.20 Subject Level Summary of Serious ADRs by Organ Class & Preferred Term

System Organ Class: Preferred Term	N=X	Intensity	Action Taken
	n (%)	Mild, Moderate, Severe	A: Dose not changed; B: Drug withdrawn.

Table 4.21 Event Level Summary of Adverse Events, Any Type

Adverse Events, Any Type	N=X n (%)
Total number of adverse event (any type)	
Intensity of adverse event, among documented adverse events (any type)	
Mild	
Moderate	
Severe	
Action taken with tirbanibulin, for documented adverse events (any type)	
Drug withdrawal / study discontinuation	
Other Actions:	
Dose Not Changed	
Number of SAEs or Serious ADRs	
Number of SAEs or Serious ADRs resulting in death	

Table 4.22 Event Level Summary of 'Not-Related to Tirbanibulin' Adverse Events

'Not-Related to Tirbanibulin' Adverse Events	N=X n (%)
Total number of 'not-related' AE	
Intensity of adverse event, among documented 'not-related' AEs	
Mild	
Moderate	
Severe	
Action taken with tirbanibulin, for documented 'not-related' AEs	
Drug withdrawal / study discontinuation	
Other Actions:	
Dose Not Changed	
Number of SAEs	
Number of SAEs resulting in death	

Table 4.23 Event Level Summary of 'Not-Related' AEs by Organ Class & Preferred Term

System Organ Class: Preferred Term	N=X	Intensity	Action Taken
	n (%)	Mild, Moderate, Severe	A: Dose not changed; B: Drug withdrawn.

Table 4.24 Event Level Summary of 'Not-Related' AEs by Patient ID

Patient ID	Study/ Survey Timepoint	Reported Term for the Adverse Event	AE Preferred Term	Primary System Organ Class	Date of Onset (yyyy/mm/dd)	Date of Resolution (yyyy/mm/dd)	Action Taken with tirbanibulin*	Intensity of Adverse Event	Is this a SAE?

Table 4.25 Event Level Summary of Adverse Drug Reactions

Adverse Drug Reactions	N=X n (%)
Total number of ADRs	
Intensity of adverse event, among documented ADRs	
Mild	
Moderate	
Severe	
Action taken with tirbanibulin, for documented ADRs	
Drug withdrawal / study discontinuation	
Other Actions:	
Dose Not Changed	
Number of Serious ADRs	
Number of Serious ADRs resulting in death	

Table 4.26 Event Level Summary of ADRs by Organ Class & Preferred Term

System Organ Class: Preferred Term	N=X	Intensity	Action Taken
	n (%)	Mild, Moderate, Severe	A: Dose not changed; B: Drug withdrawn.

Table 4.27 Event Level Summary of Serious ADRs by Organ Class & Preferred Term

System Organ Class: Preferred Term	N=X	Intensity	Action Taken
	n (%)	Mild, Moderate, Severe	A: Dose not changed; B: Drug withdrawn.

Table 4.28 Event Level Summary of ADRs by Patient ID

Patient ID	Study/ Survey Timepoint	Reported Term for the Adverse Event	AE Preferred Term	Primary System Organ Class	Date of Onset (yyyy/mm/dd)	Date of Resolution (yyyy/mm/dd)	Action Taken with tirbanibulin*	Intensity of Adverse Event	Is this a SAE?

Table 4.29 Subject Level Summary of Other Safety Events

Safety events	N=300
	n (%)

Table 4.30 Event Level Summary of Other Safety Events

Safety events	N=300
	n (%)

Table 4.31 Significant Protocol Deviations

TBD

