5.6 Safety Assessments

5.6.1 Definition of Adverse Events & Adverse Drug Reactions

An AE is any untoward medical occurrence in a patient administered a pharmaceutical product which does not necessarily have a causal relationship with this treatment. An AE can therefore be any unfavorable and unintended sign, symptom, or disease temporally associated with the use of a medicinal product, whether or not related to the medicinal product.

The Site Investigator will use the following terms to assess the severity of each AE:

- Mild: Awareness of symptoms or signs, but easily tolerated (acceptable)
- Moderate: Enough discomfort to interfere with usual activity (disturbing)
- Severe: Interferes significantly with ability to do work or usual activity (unacceptable)

A Serious Adverse Event (SAE) is any experience that suggests a significant hazard, contraindication, side effect or precaution. With respect to human clinical experience, this includes any event which:

- results in death,
- is life-threatening,

- requires inpatient hospitalization* or prolongation of hospitalization, unless hospitalization is for:
 - routine treatment or monitoring of the studied indication, not associated with any deterioration in condition.
 - elective or pre-planned treatment for a pre-existing condition that is unrelated to the indication under study and has not worsened since the start of study drug.
 - treatment on an emergency outpatient basis for an event not fulfilling any of the definitions of a SAE given above and not resulting in hospital admission.
 - social reasons and respite care in the absence of any deterioration in the subject's general condition.
- results in persistent of significant disability / incapacity, or
- is a congenital anomaly / birth defect,
- is a significant or important medical event that, based on appropriate medical judgment, may jeopardize the subject or may require intervention to prevent one of the other outcomes listed above.

* Hospitalization is defined as an overnight (in-patient) stay at the hospital or emergency room.

For all AEs (either related or not related to study medication), information about the outcome (i.e., recovered, recovering, not recovered, recovered with sequelae, fatal, unknown) and the action taken with the study treatment (i.e., drug withdrawn, dose reduced, dose increased, dose not changed, not applicable) will be documented.

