6.6.9 Safety Assessments

The safety data will be analyzed descriptively using Safety Population dataset (if it is different from FAS), to report the frequency of occurrences of AEs, SAEs, ADRs, and LSRs. These will be reported at individual item level as well in aggregate at relevant category level for Week 8

post-index date. The number of patients discontinuing treatment within the 8-week post-index date because of AEs, ADRs and for any other reasons will be reported, as documented in patient medical charts.

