Table 2.35 Patient Treatment Details, If Retreated After Week 8: Clinician Reported

Domain	Week 24 (N=x)
RMH2: I started a new AK treatment for this patient within the past 16 weeks, following patient's Week-8 visit.	
RHM2 = 2 No	n (%)
RMH2Ar1: Tirbanibulin (Klisyri®)	n (%)
RMH2Ar2: Another topical treatment	n (%)
A [OTE1r1]	
RMH2Ar3: Another treatment (which is not topical)	n (%)
A [NTR1r1]	

Note: Data from Clinician DCF, from week-24.

Table 2.36 Reason for Retreatment, If Retreated with After Week 8

Domain	Statistics	Week 24			Total
		Retreated with Klisyri® (RMH2Ar1) (N=x)	Retreated with Another Topical Treatment (RMH2Ar2) (N=x)	Retreated with Non-Topical Treatment (RMH2Ar3) (N=X)	
Why was this patient re-treated?					
1. To manage newly emerged AK lesions	n (%)	RTE1_5r1	OTE1r7r1	NTR1r7r1	
2. To re-treat original* treated AK lesions	n (%)	RTE1_5r2	OTE1r7r2	NTR1r7r2	
3. Other	n (%)	[RTE1_5r3oe]	[OTE1r7r3oe]	[NTRr7r3oe]	

Note: Data from Clinician DCF, from week-24.

Table 2.37 Area of Tirbanibulin Treatment, If Retreated with After Week-8

Character	Week 24 If retreated with Klisyri® (N=x)
AK3A1: What is the AK treatment area you have identified for the patient, to apply tirbanibulin (Klisyri®)?	
Left	
Face	n (%)
Scalp	n (%)
Right	
Face	n (%)
Scalp	n (%)
Center	
Face	n (%)
Scalp	n (%)
Unknown	
Face	n (%)
Scalp	n (%)
Overall	
Face (any area)	n (%)
Scalp (any area)	n (%)

Note: Data from Clinician DCF, from week-24.

Table 2.38 Tirbanibulin Treatment Characteristics if Retreated after Week 8

Character	Week 24 If retreated with Klisyri® (N=x)
TH1B: Prescription dose	
1. 1% tirabibanibulin, single-dose packets	n (%)
2. Other, please specify [TH1Br2oe]	n (%)
a. X	
TH1C: Prescription frequency	
1. Once daily for 5 consecutive days	n (%)
2. Other, please specify: [TH1Cr2oe]	n (%)
a. X	
RTE1_4: Treatment Status	
1. Patient completed the planned treatment course	n (%)
2. Discontinued due to treatment side-effect	n (%)
3. Discontinued due to treatment intolerance	n (%)
4. Discontinued due to lack of effectiveness	n (%)
5. Discontinued due to other reasons: [RTE1_4r5oe]	n (%)
6. Don't know / Not applicable	n (%)
RTE1_5: Why was this patient re-treated	
RTE1_5r1: To manage newly emerged AK lesions	n (%)
RTE1_5r2: To re-treat original* treated AK lesions	n (%)
RTE1_5r3: Other reason: [RTE1_5r3oe]	n (%)

Note: Data from Clinician DCF, from week-24.

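### The AE and ADR tables drop three of the five recorded drug actions and combine stopping the drug with leaving the study, and SAP 6.6.9's count of treatment discontinuations has no clear table

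*SAP*

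**What the plan says.** SAP 5.6.1 (and Protocol 8.5.1) has the action taken with study treatment documented for every AE, in five categories: "drug withdrawn, dose reduced, dose increased, dose not changed, not applicable". The shells in SAP 7.4 then use three different schemes.

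- The organ-class and preferred-term tables (4.17, 4.19, 4.20, 4.23, 4.26, 4.27) allow "A: Dose not changed; B: Drug withdrawn" and nothing else.
- The overall AE and ADR summaries (4.15, 4.16, 4.18, 4.21, 4.22, 4.25) have a row "Drug withdrawal / study discontinuation", a line "Other Actions" with no definition, and a row for unchanged dose.
- The local skin reaction table (4.13) shows all five actions under "LSR1r4 Action taken with Tirbanibulin", with drug withdrawal on its own.

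SAP 6.6.9 also promises a count by reason: "The number of patients discontinuing treatment within the 8-week post-index date because of AEs, ADRs and for any other reasons". It names the medical charts as the source.

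**The concern.** An event that begins after the last packet leaves no dose to change. If a site records it as not applicable, the organ-class tables have no code for it. If it were placed under the unchanged-dose code, it would read as an event tolerated through continued dosing.

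The combined row raises a different problem. Leaving the study is not an action taken with the drug, and Protocol 8.5.2 itself names discontinuing medication and withdrawing from the study separately. A patient who stopped on Day 2 and a patient who used all five packets and left in Week 6 could both fall in that row. Adherence and safety/tolerability are among the additional objectives, and the protocol's background links the short course to better adherence. The number who stop early because of an adverse event should therefore be readable without ambiguity.

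**Working it through.** The documents give no rate or expected count on this point, so there is no stated figure to reproduce. The check compares categories and then does simple arithmetic.

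**Inputs**
- Recorded actions: 5 (SAP 5.6.1).
- Course length: 5 days (SAP protocol summary).
- Window to Week 8: 8 × 7 = 56 days.
- Safety Population: 300 (SAP 7).
- *w*, patients who stop the drug for an AE, and *s*, patients who leave the study for an AE after completing the course: not in the documents. Both are assumed, each tried at 0, 1, 3 and 6.

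**1. Categories side by side**

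| Recorded action | Organ-class tables | Overall AE/ADR tables | Table 4.13 (LSRs) |
|---|---|---|---|
| Drug withdrawn | code B | shares a row with study discontinuation | own row |
| Dose not changed | code A | own row | own row |
| Dose reduced | none | at most the undefined other line | own row |
| Dose increased | none | at most the undefined other line | own row |
| Not applicable | none | at most the undefined other line | own row |

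Three of the five actions (5 − 2 = 3) have no code in the organ-class tables.

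**2. Dosing window.** 5/56 = 8.9%. A study exit after the fifth application cannot be early stopping of the initial course.

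**3. Do the missing codes move the withdrawal rate?** No, over a fixed denominator. With *w* = 3, 3/300 = 1.00% whether 0, 5 or 15 not-applicable events are shown as unchanged dose. The loss is of information about the other actions.

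**4. Does the combined row move it?** Drug withdrawal alone is *w*/300. The combined row can reach (*w* + *s*)/300. The difference is *s*/300:
- *s* = 0: 0.00 percentage points
- *s* = 1: 0.33
- *s* = 3: 1.00
- *s* = 6: 2.00

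For example, with *w* = 3 and *s* = 3, drug withdrawal is 3/300 = 1.00% and the combined row is 6/300 = 2.00%. If these were all ADRs, Table 4.18 could show 6 patients where code B in Table 4.19 covers 3.

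This arithmetic applies to patient counts over all 300. The shells head the action block as among patients with an event and do not fix the percentage base. On that smaller base, the same *s* gives a larger difference. The event-level tables (4.21, 4.22, 4.25) count events instead.

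**5. Where would the 6.6.9 count appear?** Tables 4.11 and 4.12 list reasons, but 4.11 places them under patient terminations and discontinuations, which appears to mean leaving the study. Tables 2.6 and 4.7 give completion of the course (item P2) as Yes or No. Table 1.5 gives the patient-reported number of missed doses without a reason. A list of reasons for stopping treatment, with entries such as "Discontinued due to treatment side-effect", appears only in Table 2.38, for re-treatment.

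**The case against.** The strongest reply is that nothing is lost and no miscount is shown. The combined row sits under a heading about action taken with the drug, so it may be filled from the AE action field alone, with study exits left to Tables 4.11 and 4.12. The undefined other line may hold the remaining categories. The patient listings, Table 4.24 and "Table 4.28 Event Level Summary of ADRs by Patient ID", give action and onset date for each event. Skin reactions, a central tolerability outcome, are kept apart from ADRs and fully tabulated in Table 4.13.

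Much of this stands. The listings make the drug-only count recoverable, and no text instructs that not-applicable events be recoded. But a row whose label names study discontinuation cannot be assumed to exclude it, and a summary promised in SAP 6.6.9 should not have to be rebuilt from listings. The reply does not reach the organ-class tables, which have no line for other actions.

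A reader might infer that the reported stopping rate will be wrong. The documents do not support that: the combined row can only equal or exceed the drug-stopping count. A reader might also infer from 5 days in 56 that most AEs start after dosing and would be misread. The documents give no distribution of onset, and events may cluster early.

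**Conclusion.** The inconsistency in the shells is established from the text: three recorded actions have no code in six organ-class tables, and six overall tables carry a combined row. The consequence is conditional. AE-related stopping read from the combined row may be overstated by *s*/300, which is 0 to 2 percentage points for assumed *s* of 0 to 6 and zero if nobody leaves the study for an AE after completing the course. This assumes that such exits are counted in the row and that percentages are taken over 300 patients. The combined row can also disagree with the drug-withdrawn code in the organ-class tables, where withdrawal stands alone. The 6.6.9 count has no clearly assigned shell. This is a reporting fault worth correcting. It does not touch the primary or secondary endpoint and implies no change to any clinical rule.

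**What to change.** 1. Show all five recorded actions in the AE and ADR summary tables, as Table 4.13 already does, so that the undefined other line is no longer needed.
2. Split the combined row into *Drug withdrawn*, taken from the AE action field, and *Study discontinuation*, taken from the termination item (P1B).
3. Add one shell for the SAP 6.6.9 count. Start from P2 = No, assign AE and ADR reasons from the AE action field, and take other reasons from the medical charts that 6.6.9 names. Do not derive the count from study termination.

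The first two are table edits on fields already recorded. The third may need chart review for patients with P2 = No and no AE-related withdrawal. Attaching the reason list in Table 2.38 to the initial course is not proposed: that would be new data collection and may no longer be possible. The price is slightly longer tables.
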